1.1.5 Nanostring platform for gene expression analysis of formalin-fixed paraffin embedded tumor

Gene expressing profiling performed by the nanostring technology, which utilizes formalin-fixed paraffin embedded (FFPE) tissue using the nCounter® appears highly promising (82). This technology provides robust data from FFPE tissue using the nCounter® GX Kit and offers high levels of precision and sensitivity (>1 copy per cell) without the need for amplification of ≥ 100 ng of RNA. Nanostring is a multiplexed (up to 800 genes per reaction) platform, which utilizes digital counting and excellent quantitative reproducibility by employing two ~50 base probes per mRNA that hybridize in solution. Multiple successful applications utilizing the nCounter System to subtype tumors, formulate tumor prognostic signatures, or discover novel targets for therapy have been reported in other malignancies (83-86). Notably, the 50-gene PAM50 signature (Prosigna™) derived from nanostring was approved by the US FDA in 2013 to assess the risk of distant recurrence at 10 years in postmenopausal women with hormone receptor-positive breast cancer. Indeed, the PAM50 gene score, which is enriched for proliferation-associated genes appeared more robust than the Oncotype DX® recurrence score in predicting recurrence (85).

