3.4 Exploratory tumor tissue studies and central pathology review

Archival formalin-fixed paraffin-embedded (FFPE) tumor slides will be obtained for central pathology review and molecular studies. Fifteen slides of 10 μ M thickness sections each and 5 slides of 5 μ M thickness sections each will be obtained. Following central pathology review for determining histologic subtype, tumor will be demarcated from adjacent normal tissue on the H+E slide to guide procurement of tumor-enriched samples. The 10 μ M sections will be used for RNA isolation toward gene expression profiling for ~800 cancer-promoting, kinase, DNA-damage repair, bladder cancer-specific and stem cell panel genes by the nanostring platform performed centrally at UAB Cancer Center. A total surface area of tumor 100 mm² is adequate to harvest the necessary amount of RNA (100 ng) using the RNAeasy Mini Kit (Qiagen), and the quality of the RNA will be assessed via the 260/280 ratio using nanodrop. [name] at UAB Radiation Oncology Dept. will perform the nanostring studies as described in previous publications utilizing the nCounter by inputting RNA directly into a hybridization reaction containing color-coded molecular barcodes representing the genes of interest [56].

A minimum of 100 ng of genomic double-stranded DNA (dsDNA) will be isolated from tumor alone for restoration and downstream applications. Genomic DNA will then be isolated using the QIAamp DNA FFPE Tissue Kit on the QIAcube robotic platform (QIAgen, Germantown, MD). dsDNA is quantified using the QuantiT Pico Green dsDNA kit (Invitrogen, Carlsbad, CA) and quality control (QC) is performed by the Illumina FFPE QC kit and real time PCR. If the DNA passes the required QC threshold (5 CT within the QC positive control), the restoration will be performed by using the Infinium HD FFPE Restore kit (Illumina, San Diego, CA). Real time PCR probes for the HPV16 and HPV18 E6 region will be designed using the GeneAssist Copy Number Assay design tool (Invitrogen). Real time PCR quantification of viral load will then be performed using 100 pg of genomic DNA, the HPV16 and HPV18 primer/probe sets and eukaryotic 18S primer/probe set as normalizer in separate reactions. HPV viral load is then calculated as HPV16E6/18S and HPV18E6/18S.

Immunohistochemistry (IHC) will be performed on the 5µM section slides for EGFR, Her2, Her3 and Her4 by previously described methods using appropriate controls.

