7.3 Planned analyses

This trial will be conducted with Intention-To-Treat and all patients for whom PFS6 is evaluable and can be calculated will be included in the final analysis for estimating progression free survival. Statistical significance will be defined as a p-value < 0.05 .

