NanoString technology will be applied to measure the expression of candidate cancer and kinase genes that may predict outcomes and benefit from Gilotrif, and six internal reference genes (101). The nSolver text files (.csv) and NanoString .rcc files will be imported into Partek Genomic Suite 6.6 (PGS, Saint Louis, MO) for statistics and bioinformatics analysis. The differential expressions are determined by ANOVA. A gene list is then created after false discovery rate (FDR) p value correction by Benjamini and Hochberg method (102). Further functional analysis including gene-gene interactions and signaling pathways will be conducted by using Ingenuity Pathway Analysis (IPA, Redwood City, CA). Due to small study numbers, exact logistic regression models will be used to explore whether tumor biomarker (EGFR, Her2, Her3, Her4, nanostring gene expression) expression predicts for response and freedom from progression. Prognostic impact of gene expression, HPV status and IHC studies will be performed using Cox proportional hazards regression. Variables of interest will be evaluated after adjusting for performance status and presence of visceral metastases. Impact of statistically significant variables will be described using hazard ratios, 95% confidence intervals, and concordance statistics. These results are hypothesis-generating and will require external validation.

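### False discovery rate control is written only for the ANOVA gene list; the logistic and Cox models that link gene expression to outcome have no stated error control, and the genes entering them are not defined

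*Combined protocol and SAP*

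**What the plan says.** Section 3.4 of the combined protocol and SAP plans "gene expression profiling for ~800 cancer-promoting, kinase, DNA-damage repair, bladder cancer-specific and stem cell panel genes". Section 1.1.5 gives the platform's capacity in line with that: "Nanostring is a multiplexed (up to 800 genes per reaction) platform".

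Section 7.3.2 describes the gene analysis in this order:

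- Differential expression is assessed by ANOVA. The grouping variable is not named.
- "A gene list is then created after false discovery rate (FDR) p value correction by Benjamini and Hochberg method". No FDR level is given.
- Exact logistic models explore whether the IHC markers and NanoString expression predict response and freedom from progression.
- "Prognostic impact of gene expression, HPV status and IHC studies will be performed using Cox proportional hazards regression". The time-to-event outcome is not named.
- Variables of interest, not further defined, are adjusted for performance status and visceral metastases. The significant ones are described by hazard ratios, confidence intervals and concordance statistics.

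The section closes by calling the results hypothesis-generating and in need of external validation. The only significance threshold for the planned analyses is in Section 7.3: "Statistical significance will be defined as a p-value < 0.05".

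**The concern.** The sponsor evidently judged that a panel of this size needs false discovery rate control, because it is specified for ANOVA. The results a reader will use, however, are the odds ratios and hazard ratios from the later models, and there the correction is not repeated. Significance also acts as the reporting filter, so the threshold decides which genes are presented.

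What is at stake is how the gene list can be read. Without a stated error rate, someone choosing genes for the external validation that the plan asks for cannot tell how many of those listed would be expected by chance.

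**Working it through.** **Inputs.** About 800 genes (Section 3.4). Six internal reference genes (Section 7.3.2), so 794 to 800 tested if they are inside the count. Threshold 0.05 (Section 7.3). 27 evaluable patients (Section 7.5). Success rule of at least 4 of 27 (Section 7.3.1).

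**The plan's own figure.** The documents give no expected number of false-positive genes. The one related design figure, power of 80.1%, reproduces: the sum over x = 1 to 13 of P(Bin(13, 0.20) = x) × P(Bin(14, 0.20) ≥ 4 − x) is 0.8011. The same sum at 0.05 gives a one-sided alpha of 0.0416. The design implies few successes for the logistic models: 27 × 0.05 = 1.35 expected under the null rate and 27 × 0.20 = 5.4 under the alternative.

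**Reading 1: the whole panel enters the models.** With no true association, expected chance flags = number of genes × actual test size.

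- Nominal: 800 × 0.05 = 40 per outcome (794 × 0.05 = 39.7). Correlation between genes leaves this mean unchanged but widens the spread.
- Exact logistic, continuous expression, 4 successes: simulated size 5.3%, or 42 genes. This is the nominal 5% within simulation error.
- The same, adjusted for two binary covariates: 4.1%, or 33 genes.
- Exact logistic, median split, 4 successes: 0 genes with doubled-tail p-values, 33 with point-probability p-values.
- Exactly 1 success: the smallest doubled-tail p is 2/27 = 0.074, so 0 genes.
- Cox model adjusted for two covariates, 27 patients: simulated size 6.9% (Wald) to 7.1% (likelihood ratio), or 55 to 57 genes. This assumes 50% prevalence for each covariate, exponential survival, a log hazard ratio of 0.7 for each covariate, and a fixed censoring time. With 1,500 simulated trials the standard error is about 5 genes (800 × √(0.071 × 0.929/1500) = 5.3).

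The range is therefore 0 to about 57 per outcome around a nominal 40.

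**With Benjamini-Hochberg across 800 genes.** At an assumed level of 0.05, with independent genes and no true association, the simulated probability of flagging any gene is about 0.05, and the mean number flagged is about 0.05 per outcome.

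**Reading 2: only the ANOVA list enters.** Call its length L.

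- If the ANOVA groups are outcome groups, the logistic step re-tests genes on the outcome that selected them, in the same patients. Its p-values and effect estimates carry selection bias.
- If the groups are something else, such as HPV status, ANOVA error control says nothing about association with response, freedom from progression or the Cox outcome. At p < 0.05, L genes give nominally up to 0.05 × L chance flags per outcome, for example 0.05 × 50 = 2.5 for an assumed list of 50.

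**What correction costs in the logistic step.** The top gene must reach 0.05/800 = 0.0000625 to pass alone. The smallest unadjusted doubled exact p-value, at perfect separation, is 2/C(27, k) for k successes:

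| Successes | Smallest p | Genes that must tie at that p to pass |
|---|---|---|
| 5 | 2/80,730 = 0.000025 | 1 |
| 4 | 2/17,550 = 0.000114 | 2 |
| 3 | 2/2,925 = 0.00068 | 11 |
| 1 | 2/27 = 0.074 | cannot pass |

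**The case against.** The strongest reply is that the order of the text in Section 7.3.2 can be read as a pipeline: genes are measured, ANOVA and the FDR step produce a list, and that list supplies the variables of interest for the later models. No sentence sends all 800 genes into the logistic or Cox models. That stands. A reader might infer that the plan will flag about 40 false genes per outcome; the documents do not support that as a flat prediction. It needs the whole panel to be tested, no gene to matter and an actual test size of 5%. A reader might also infer that the reported genes would be mostly noise. That cannot be derived, because it depends on how many genes are truly associated, which the documents do not give.

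The p < 0.05 sentence in Section 7.3 also follows directly on the description of the progression-free survival analysis, so its reach to gene-level tests is by default. It is nevertheless the only threshold stated, and the biomarker models sit under the same section.

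The tissue studies are exploratory, and external validation is a genuine guard against false leads. This limits the consequence. It does not supply an error rate for the list.

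Finally, correction is not free: with 4 or fewer successes, one perfectly separating gene could not pass alone. That stands for the logistic step. It does not extend to the Cox step in the same way, and reporting raw p-values and estimates beside q-values keeps the information.

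**Conclusion.** The gap is real on either reading: the FDR control as written does not cover the logistic and Cox results. Its size depends on a choice the plan leaves open. With the whole panel tested at p < 0.05 and no true association, nominally 40 genes per outcome would be called significant by chance, and about 0 to 57 by calculation. With only the ANOVA list, the count depends on its unknown length and on the unnamed ANOVA grouping.

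These figures rest on 27 patients all having usable expression data, the assumed Cox scenario for the upper end, and an FDR level of 0.05 that the plan does not state. The point concerns exploratory analyses only. The go/no-go rule, the primary endpoint and the safety summaries do not use a gene result. It is a cheap improvement to the plan, not a threat to the trial's main conclusion.

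**What to change.** Amend Section 7.3.2 to:

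- state which genes enter each model (whole panel, ANOVA list or a named subset), and name the ANOVA grouping variable and the Cox outcome so that each family of tests is defined;
- apply Benjamini-Hochberg across all genes tested within each model family (ANOVA, exact logistic, Cox) and each outcome, at a stated FDR level;
- report q-values beside raw p-values and effect estimates;
- base the label of statistical significance for genes on the FDR level, not on p < 0.05;
- treat EGFR, Her2, Her3, Her4 and HPV as a separate, small, pre-named family.

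If only the ANOVA list enters and its groups are outcome groups, the report should also say that the later p-values and estimates come after selection in the same patients.

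The cost is SAP wording, with no new data or patients. Fewer genes will be labelled significant, and with about 4 or fewer successes in 27 the exact logistic step may be able to flag almost none. The SAP should acknowledge this, so that an empty list is not read as evidence that no gene matters.

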7.3.2 Secondary analyses

The secondary endpoints are not formally powered for, but will be examined in the evaluable population. RECIST responses, regression and toxicities will be analyzed as secondary endpoints. Descriptive statistics including frequencies and proportions will be calculated to summarize safety and toxicity outcomes. Specifically, the number of adverse events (AE) and serious adverse events (SAE) will be tabulated and summarized. Point estimates and two-sided, exact binomial (Clopper-Pearson) 95% confidence intervals (CI) will be calculated to estimate the incidence of AEs and SAEs. The precision of these estimates, i.e., width of the confidence interval, will depend on the estimated incidence of each outcome. The table below gives the exact 95% confidence intervals for a range of incidences, assuming 27 evaluable subjects.

Number of subjects experiencing event	Estimated Incidence	95% Exact CI for Incidence		Width of CI
		Lower Limit	Upper Limit	
1	0.037	0.001	0.190	0.189
2	0.074	0.009	0.243	0.234
4	0.148	0.042	0.337	0.295
7	0.259	0.111	0.463	0.352

14	0.519	0.319	0.713	0.394
----	-------	-------	-------	-------

The Kaplan-Meier method will be used to estimate OS rates over time with standard errors estimated using Greenwood's formula. Chi-square or Fisher's exact test will be employed to determine bivariate association of biomarker status with PFS6 and objective response.

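### Section 7.3.2 ties Cox hazard ratios to statistical significance, so in at most 27 evaluable patients those reported will be exaggerated on average

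*Combined protocol and SAP*

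**What the plan says.** Section 7.3.2 plans several biomarker analyses. For prognosis it says "Prognostic impact of gene expression, HPV status and IHC studies will be performed using Cox proportional hazards regression", and it adds "Variables of interest will be evaluated after adjusting for performance status and presence of visceral metastases". The reporting sentence follows: "Impact of statistically significant variables will be described using hazard ratios, 95% confidence intervals, and concordance statistics". Section 7.3 supplies the threshold: "Statistical significance will be defined as a p-value < 0.05".

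Three neighbouring provisions bear on the point:

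- "Chi-square or Fisher's exact test will be employed to determine bivariate association of biomarker status with PFS6 and objective response". This carries no significance condition, and neither do the exact logistic models that name EGFR, Her2, Her3, Her4 and gene expression.
- "A gene list is then created after false discovery rate (FDR) p value correction by Benjamini and Hochberg method". This is attached to the ANOVA gene list; Section 7.3.2 does not extend it to the Cox models.
- The biomarker paragraph closes with "These results are hypothesis-generating and will require external validation".

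Section 3.4 gives the number of candidates: "gene expression profiling for ~800 cancer-promoting, kinase, DNA-damage repair", besides the four IHC markers and HPV. The time-to-event endpoint for the Cox models and the expected number of events are not stated.

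**The concern.** The reporting sentence is the plan's sole statement on how Cox effect sizes will be presented, and it covers significant variables. An analyst following it literally could give a hazard ratio for a marker at p=0.04 and none for a marker at p=0.06.

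When events are few, an estimate reaches significance by being far from 1. The hazard ratios that pass are therefore a selected set and overstate the effect on average. Concordance computed in the patients used to fit the model is optimistic as well, and no internal validation is planned.

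The declared purpose is to produce hypotheses for outside validation. An inflated hazard ratio is a poor basis for sizing that work. A marker left without an estimate and interval cannot be pooled with other data, which matters in a disease that the protocol describes as too rare for large randomised trials (Section 1.1.3).

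**Working it through.** **The plan's own figure.** The plan gives no figure for the biomarker models. Its design figure reproduces: stopping at 0/13 and requiring at least 4/27 gives exact power 0.8011 at a PFS6 of 20% (stated 80.1%) and type I error 0.0416 at 5%. Nothing below alters it.

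**Inputs from the document.** 27 evaluable patients, 13 in stage 1 (Section 7.1); p<0.05 (Section 7.3); two adjustment covariates (Section 7.3.2).

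**Assumptions.** Two-sided testing, to match the 95% interval; a binary marker with prevalence *a*; *d* events from 20 to 27; true hazard ratios from 1 to 3.

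**Step 1: smallest significant estimate.** SE(log HR) = 1/√(d·a·(1−a)), and the threshold is exp(1.96 × SE).

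| Events | Prevalence | SE | HR threshold |
|---|---|---|---|
| 27 | 50% | 0.385 | 2.13 (or 0.47) |
| 27 | 20% | 0.481 | 2.57 |
| 25 | 50% | 0.400 | 2.19 (or 0.46) |
| 20 | 50% | 0.447 | 2.40 |
| 20 | 20% | 0.559 | 2.99 |

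If the trial stops after stage 1 and all 13 patients have events, an approximately even split gives SE = 2/√13 = 0.555 and a threshold of about 2.97.

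**Step 2: average of the estimates that pass, 25 events and an even split (SE 0.40).** With c = 1.96 − log(HR)/SE, the chance of significance in the true direction is 1 − Φ(c), and the mean log HR given significance is log(HR) + SE·φ(c)/(1 − Φ(c)).

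- True HR 1.5: c = 1.96 − 0.405/0.40 = 0.946. The chance is 0.172 (0.173 counting both directions). The mean is 0.405 + 0.40 × 0.255/0.172 = 0.998, an HR of 2.71.
- True HR 2.0: c = 1.96 − 0.693/0.40 = 0.227. The chance is 0.410. The mean is 0.693 + 0.40 × 0.389/0.410 = 1.072, an HR of 2.92.
- True HR 3.0: c = 1.96 − 1.099/0.40 = −0.787. The chance is 0.784. The mean is 1.099 + 0.40 × 0.293/0.784 = 1.248, an HR of 3.48. About 36% of the significant estimates lie below 3.0.

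When the true HR is below the threshold, every significant estimate in its direction must exceed it. Above the threshold, exaggeration holds on average and not in each case.

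**Step 3: check with the planned adjustment.** The simulation used 2,000 Cox fits per scenario, 27 patients, a 13/14 marker split, no censoring and two covariates (assumed prevalences 60% and 50%, HR 1.8 each). Averages are geometric means; the last column ignores direction.

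| True HR | Significant | Average, all fits | Average, significant fits |
|---|---|---|---|
| 1.0 | 7% | 0.99 | 3.17 |
| 1.5 | 19% | 1.58 | 3.45 |
| 2.0 | 41% | 2.23 | 3.65 |
| 3.0 | 72% | 3.50 | 4.46 |

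All significant estimates exceeded the truth in magnitude at 1.5 and 2.0; 81% did at 3.0. Small-sample bias explains the drift in the third column. The gap between the last two columns comes from selecting on significance.

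**Step 4: consequence for a follow-on study.** Required events scale as 1/(log HR)². Planning on 2.71 when the truth is 1.5 gives (0.405/0.997)² = 0.17 of the events needed. Planning on 2.92 when the truth is 2.0 gives (0.693/1.072)² = 0.42.

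**The case against.** The strongest reply is textual. The sentence says how significant variables will be described; it does not say that other estimates will be withheld, and the Cox models themselves are planned without any significance condition. A reader might infer that hazard ratios will be given for significant markers alone and that null results will be hidden. The documents do not support that. They are silent on non-significant Cox results, and the Fisher and exact logistic analyses are unfiltered, so EGFR and the HER markers appear in a model with no such condition. What stands is narrower: no commitment to report the Cox estimates exists, and the unfiltered analyses do not yield time-to-event hazard ratios.

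A reader might also infer that exaggeration is guaranteed for every reported marker. It is not: at a true hazard ratio of 3, about 36% of significant estimates fall below the truth in the unadjusted approximation, and about 19% in the adjusted simulation.

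The false discovery rate step and the hypothesis-generating label are real safeguards against over-claiming. Neither removes the selection: the former is stated for the ANOVA list, and a stricter cut-off raises the size an estimate needs to pass. It is also fair that no validation study is planned or sized here, so Step 4 is illustrative, and that the thresholds apply to a binary marker. For continuous expression, a hazard ratio cut-off depends on the measurement unit.

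**Conclusion.** The point holds as a reporting weakness confined to the Cox biomarker analyses. As written, the rule yields hazard ratios that are exaggerated on average, and always so when the true value is below a threshold of about 2.1 (27 events, even split) to about 3.0 (20 events, 20% prevalence). With 25 events and an even split, a true 1.5 would be significant about 17% of the time and average about 2.7; a true 2.0, about 41% and about 2.9. These figures rest on assumed event counts, prevalence and two-sided testing, and on an unadjusted approximation; the adjusted simulation shows larger inflation. The analyses are exploratory. The sample size, the PFS6 decision rule and its conclusion, and the safety results are untouched, so this is a cheap improvement and not a flaw in the design.

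**What to change.** Replace the reporting sentence in Section 7.3.2 with: *Adjusted hazard ratios and 95% confidence intervals will be reported for every pre-named marker (EGFR, Her2, Her3, Her4, HPV status) regardless of p-value.* Label any concordance statistic as apparent, that is, not internally validated. It would help to name the Cox endpoint and give the number of events beside the estimates.

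The cost is a little more tabulation, and some wide intervals will be shown. Extending the commitment to all of the roughly 800 genes, or adding bootstrap-corrected concordance, would be less simple: three-covariate Cox fits in at most 27 patients may be unstable, and an honest correction would have to repeat the selection step in each resample. The change proposed here does not depend on either.

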Pathologic TNM staging provides prognostic stratification after surgery (31). Furthermore, extranodal extension in inguinal LNs and pelvic LN involvement appear to be independently associated with decreased 5-year cancer specific survival (42% and 22%, respectively) (32). Nomograms have been reported for patients following penectomy to better predict cancer-specific survival and LN metastasis (33-35). These nomograms incorporate multiple variables in addition to stage to enhance prognostication including grade, venous or lymphatic embolization and type of surgery. Other studies have reported lymph node density, lack of koilocytosis and clear cell subtype to be prognostic (32, 35-49). In patients with locally advanced and advanced disease undergoing systemic first-line chemotherapy, a recent analysis identified performance status and visceral metastasis as major prognostic factors (50). In this retrospective analysis of 140 men receiving first-line chemotherapy, the multivariate model of poor prognostic factors included visceral metastases ($p<0.001$) and ECOG-PS ≥ 1 ($p<0.001$) for both PFS and OS. A risk model showed that those with 0, 1 and both poor prognostic factors which was internally validated and demonstrated moderate discriminatory ability (c-statistic of 0.657 and 0.677 for OS and PFS). The median OS for the entire population was 9 months. Median OS was not reached, 8 and 7 months respectively for those with 0, 1 and both risk factors. Cisplatin-based regimens were associated with better OS ($p=0.017$), but not PFS ($p=0.37$), compared to non-cisplatin based regimens after adjusting for the 2 prognostic factors.

Additionally, molecular prognostic markers are suggested by some studies, e.g. p53, ki-67, E-cadherin, MMP-9, Annexins I and IV and decreased KAI1/CD82, a metastasis suppressor gene (21, 23, 51-54). Although HPV has been associated with high-grade tumors, the impact on outcomes is unclear with one study even demonstrating a favorable impact of HPV and another study showing a positive association with survival of p16, which is related to HPV (10, 55-57).

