7. STATISTICAL METHODS AND DETERMINATION OF SAMPLE SIZE

7.1 Statistical design-model

Given the poor prognosis of this patient population and data from other studies of salvage therapy, a PFS6 of $\geq 20\%$ is considered to be important for this regimen, while a PFS6 $< 5\%$ will be considered to be of poor interest. A two-stage minimax design will be used which will enroll a maximum of 27 subjects: 13 during stage 1 and 14 during stage 2. If no patients are free from progression at 6 months among 13 patients during the first stage, then the trial ends with the conclusion that this drug is not worth further study. Otherwise the trial proceeds to the second stage. Since some (5-10%) accrued patients may not be evaluable, up to 29 patients will be enrolled.

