7.2 Null and alternative hypotheses

The null hypothesis for this study is that PFS at 6 months will occur in less than 5% after treating with Gilotrif whereas the study alternative hypothesis is that PFS at 6 months will be observed in 20% or more of all patients, which will signify important activity of Gilotrif in this patient population.

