7.5 Determination of sample size

SAS version 9.3 was used to calculate power and determine sample size. The justification for the proposed sample size is based on applying an exact test for a binomial proportion to Simon's two-stage minimax design(103). A one-sided significance level of 5% was used. Under this design, we will have approximately 80% power (80.1%) to reject the null hypothesis that $PFS < 5\%$ in favour of $PFS6 \geq 20\%$.

A total of up to 29 patients will be enrolled including 27 evaluable patients for this trial. Accrual period will be ~12 months. Follow-up will be at least 6 months after the last patient starts therapy. Thus, the overall duration of the trial is expected to be ~18 months.

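### Concordance statistics for significant biomarkers are in-sample, uncorrected and not tied to a stated model, so they can overstate what a marker adds (minor, exploratory)

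*Combined protocol and SAP*

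**What the plan says.** Section 7.3.2 of the combined protocol and SAP fits Cox models for gene expression, HPV status and IHC. On the covariates it says: "Variables of interest will be evaluated after adjusting for performance status and presence of visceral metastases". Variables that turn out statistically significant are then described with "hazard ratios, 95% confidence intervals, and concordance statistics". Section 7.3 sets significance at p<0.05.

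The candidates are numerous. Section 3.4 plans about 800 genes, four IHC markers and HPV status. Section 7.3.2 applies Benjamini-Hochberg correction to the ANOVA gene list, gives no FDR level, and does not say that the correction covers the Cox models. The biomarker paragraph ends by calling the results hypothesis-generating and in need of confirmation in outside data.

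No section mentions a hold-out set, cross-validation, bootstrap or optimism correction, or a comparison with a model that omits the marker.

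Section 1.1.2 cites, as background, a risk model from 140 men on first-line chemotherapy. It uses the same two clinical factors, "which was internally validated and demonstrated moderate discriminatory ability (c-statistic of 0.657 and 0.677 for OS and PFS").

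**The concern.** A C-statistic computed in the patients who supplied the coefficients is biased upward. The bias grows when the number of events is small relative to the number of terms, and grows again when only markers that passed a significance test in those patients are described. Both conditions apply here: at least three terms, about 20-25 events, and a filter at p<0.05.

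A second problem is attribution. If C is for the adjusted model, some of it belongs to performance status and visceral metastases. Without the C of the two-factor model beside it, a reader cannot see what the marker contributes.

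What is at stake is the choice of marker to carry forward. The reported C would help decide which one merits a validation study, and a marker that adds nothing could look useful.

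**Working it through.** **1. The plan's own figure.** The documents give no design figure for concordance. The only design calculation is for the primary endpoint, with stages of "13 during stage 1 and 14 during stage 2", stopping at 0 of 13 and success at 4 or more of 27:

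P(success) = P(X27 ≥ 4) − P(X13 = 0) × P(X14 ≥ 4)

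At a PFS6 rate of 20%: 0.8177 − 0.0550 × 0.3018 = 0.801, which matches the 80.1% in Section 7.5. At 5% the same formula gives a type I error of 0.0416, within the one-sided 5%. The primary design reproduces, and nothing below affects it.

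**2. Inputs for the concordance check.**
- From the documents: 27 patients; two adjusters; p<0.05; median PFS 11 weeks and OS 23 weeks from the second-line paclitaxel trial (Section 1.1.3); about 12 months of accrual with at least 6 months of follow-up (Section 7.5), hence censoring between 6 and 18 months.
- Assumed: exponential times, uniform censoring, independent markers, adjuster prevalence of 50-60%, adjuster hazard ratios from 1 to 2.7.

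Harrell's C = (concordant pairs + ½ tied pairs) / usable pairs. Every simulated marker has no effect, so its true stand-alone C is 0.50.

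**3. One null marker, n=27** (2,000 trials per scenario, adjuster hazard ratio 1 or 2).

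| C reported for | PFS-like, about 25 events: mean C | share ≥ 0.677 | OS-like, about 20-21 events: mean C | share ≥ 0.657 |
|---|---|---|---|---|
| Adjusted model, marker passed p<0.05 | 0.66-0.70 | 34-68% | 0.68-0.72 | 65-89% |
| Marker alone, passed p<0.05 | 0.60-0.62 | 1-9% | 0.61-0.65 | 10-39% |

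Without the significance filter, the marker alone averages 0.54-0.55, and at most 1% reach 0.677 with PFS-like times. If tissue loss left 20 patients (an assumption), the filtered means rise to 0.69-0.75 (adjusted) and 0.63-0.66 (alone).

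**4. Best of five null markers, n=27.** The best marker was significant in 24-31% of trials. In those trials the adjusted model scored 0.70-0.76 in sample and 0.55-0.63 in new patients. The two clinical factors alone scored 0.58-0.66. The true increment is therefore about 0.55 − 0.58 = −0.03, or 0.63 − 0.66 = −0.03: the marker makes prediction slightly worse while the apparent increment is about 0.06-0.09.

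**5. 800 null genes at nominal p-values** (40 trials per scenario, PFS-like). An exact test would pass 800 × 0.05 = 40 genes; the Wald test at this size passed about 55-57. The best gene's adjusted model averaged 0.74-0.76 in sample, and 98-100% of trials reached 0.677. In new patients it scored 0.50 (adjusters without effect) or 0.57 (hazard ratio 2). The two factors alone scored 0.61 at hazard ratio 2.

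**6. How much of C is the two factors.** With no marker, the two-factor model already averages 0.62-0.63 in sample at hazard ratio 1.8. It averages 0.67-0.69 at hazard ratios of about 2.5-3, the values needed to match the cited C. One unselected null marker adds only about 0.02.

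**7. Does bootstrap correction work?** Corrected C = apparent C − mean over resamples of (C in resample − C of that resample's model in the original data), with selection repeated each time.
- Five null markers, adjusters without effect, all trials (60 trials, 60 resamples): 0.636 falls to 0.546, truth 0.50. Share of optimism removed: (0.636 − 0.546) / (0.636 − 0.50) = 0.090 / 0.136 = 66%. The share at or above 0.677 falls from 17% to 0%.
- Only trials with a significant null marker (21 trials, 60 resamples, hazard ratio 1.8): 0.69 falls to 0.62, truth 0.56. Share removed: 0.07 / 0.13 = 54%.
- Increment over the base model, significant null markers: about 0.06-0.09 falls to 0.02-0.06, truth about −0.03.

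**The case against.** The strongest reply is that the plan has already answered this. The sentence after the one at issue calls the results hypothesis-generating and asks for external validation, which is a better remedy than any resampling of 27 patients. The biomarkers are exploratory objectives (Section 2.2.3), and neither the stopping rule nor the success rule uses them. The gene list has an FDR step. All of that stands, and it caps the importance of the point. It does not correct the number that would be printed, and fewer false selections would not make an in-sample C unbiased.

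The reply is also right that the size depends on which C is meant. The plan does not say, so it cannot be charged with crediting the marker for the adjusters' discrimination; it only leaves that possibility open.

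A reader might infer that a useless marker will generally look as good as the cited risk model. The documents do not support that:
- With five candidates and hazard ratio 1.8, about 30% of trials have a significant null marker and 76% of those reach 0.657, so 0.30 × 0.76 = 23% of trials.
- A null marker judged alone usually stays below 0.657 and 0.677.
- The two factors can come near those values in sample with no marker at all.
- The cited C values are background from first-line patients. Section 7 never uses them as a comparator, this trial enrols pretreated men, and the cited model is described as internally validated only.

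Finally, the bootstrap is an imperfect remedy, as step 7 shows. That is why the base-model comparison and the label matter as much as the correction.

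**Conclusion.** The concern holds as a minor point about an exploratory analysis. As written, Section 7.3.2 yields a C-statistic that is in-sample, conditional on significance in the same patients, and attached to no stated model. Under the adjusted-model reading, the gap between the reported value and performance in new patients is of the order of 0.1 or more for a null marker that passes the filter: about 0.66-0.76 against about 0.50-0.63. Under the marker-alone reading it is about 0.60-0.65 against a true 0.50.

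The direction does not depend on the assumptions. The size does, because the adjusters' hazard ratios and prevalences, the censoring pattern, marker independence and the number of candidates actually tested are not in the documents. The near-certain inflation with 800 genes applies only if nominal p-values decide which genes are described, which the plan leaves open.

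**What to change.** In Section 7.3.2:
1. State whether C refers to the marker alone or to the adjusted model.
2. Report the C of the base model (performance status plus visceral metastases), the C of the model with the marker, and the difference.
3. Write down the selection rule, including whether the FDR step governs entry to the Cox models. Give bootstrap optimism-corrected values for both models, repeating that rule in each resample.
4. Label any uncorrected value as apparent.
5. State that correction after significance selection at this sample size removes only part of the optimism.

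No new data are needed: a few lines of text and code, plus modest extra computing if selection covers the roughly 800-gene panel. The downside is that the reported C values will be lower and visibly imprecise.
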